# 1. INTRODUCTION

Choroideremia is a degenerative retinal disease for which gene transfer research is in progress, including a clinical trial in the United Kingdom (MacLaren *et al.*, 2014). This X-linked disease of males is characterized by deletions or mutations in the choroideremia gene (*CHM*) at Xq21.2, resulting in defective or absent Rab escort protein-1 (REP-1), the encoded protein of the *CHM* gene (Nussbaum *et al.*, 1985; Seabra *et al.*, 1993; Seabra *et al.*, 1995; Cremers *et al.*, 1994; Alexandrov *et al.*, 1994). Absence or deficiency of REP-1 due to deletions or mutations in the *CHM* gene leads to cellular apoptosis and degeneration of the retinal pigment epithelium (RPE), choroid, and retinal photoreceptors. Although in normal retinas, the *CHM* gene is expressed in multiple cell types, including retinal pigment epithelium, photoreceptors and choroidal cells, there is evidence that the RPE cell is the primary disease causing cell type. The AAV serotype 2 vector, which targets RPE cells primarily (and other retinal cell types secondarily) is thus an ideal vector for choroideremia.

Clinically, choroideremia is diagnosed in affected males who manifest night blindness in childhood, followed by progressive constriction of visual fields, usually symptomatic in their teenage years, and eventual total blindness. The pathological hallmarks of the disease are degeneration of the choroicapillaris, as well as retinal pigment epithelium and photoreceptors (MacDonald *et al.*, 2009). The disease course is variable, with early manifestations of decreased dark adaptation, progressing to decreased peripheral vision, followed eventually by loss of central vision, generally occurring later in life. In some patients, blindness occurs after a prolonged course. The rationale for a gene transfer approach for choroideremia is that a corrective gene delivered to the RPE early enough in the clinical course may halt degeneration and restore the RPE, retinal vasculature, and photoreceptors.

This clinical study proposes to deliver the normal human *CHM* gene (hCHM) to the subretinal space using AAV2-hCHM, a single stranded AAV vector, based on several considerations.

This document details the statistical methods planned to perform the final analysis, as well as the interim Data Safety Monitoring Board (DSMB) analyses, of the Protocol AAV2-hCHM-101 study. The study is designed primarily to evaluate the safety and tolerability of subretinal administration of AAV2-hCHM, in an inter-subject group dose escalation in individuals with choroideremia.

# 2. **OBJECTIVES AND EVALUATIONS**

### 2.1 Objectives

### 2.1.1 Primary Objective

The primary objective of this study is:

• To evaluate the safety and tolerability of subretinal administration, in an inter-subject group dose escalation, of AAV2-hCHM in adults with choroideremia.

### 2.1.2 Secondary Objectives

The secondary objectives of this study are:

- To define the dose of AAV2-hCHM required to achieve stable, or improved visual function and functional vision in subjects with choroideremia.
- To characterize the immune responses to the *CHM* transgene protein product (REP-1) and AAV2 capsid proteins following subretinal administration of AAV2-hCHM.

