The investigative team is not certain if the mild focal loss of photoreceptors observed in two of four eyes injected with the high dose of AAV2-hCHM and sacrificed at day 91 was due to complications of the subretinal injection, the AAV2 capsid, or expression of human REP-1 in cynomolgus monkeys. Since similar and higher doses of AAV2-hRPE65v2 did not lead to photoreceptor loss when injected into the eyes of this same species of monkeys, this finding is not likely due to the AAV2 capsid. However, it is possible that it could be due to expression of a foreign transgene, as there are 18 amino acid differences between the human and cynomolgus REP-1 proteins, while there is only a single amino acid difference between the human and cynomolgus hRPE65 proteins. Thus, it is more likely that the hREP-1 protein will be viewed as a foreign antigen than hRPE65.

In the Phase 1/2 clinical trial, reaction to the human REP-1 transgene product is less likely. The investigative team believes the results obtained in the NHP study support the use of two dose levels in the proposed Phase 1/2 clinical trial, namely  $5x10^{10}$  vg/eye and  $1x10^{11}$  vg/eye.

In a separate NHP study, one cynomolgus monkey for each of the dose groups  $(5x10^{11}, 7.5x10^{11}, and 2x10^{12} vg per eye)$  received AAV2-hCHM via bilateral subretinal injections (Couto, 2016 ARVO Meeting; Ignatova, 2016 ASGCT Meeting). Retinal tissues from the

vector exposed area (bleb), as well as from outside the bleb area, were harvested 30 days after the injection. Retina tissues from three uninjected NHPs were used as control in a speciesspecific quantitative Reverse Transcription Polymerase Chain Reaction (RT-PCR) assay. Human REP-1 expression was observed at robust levels within the bleb area and at very low levels outside the bleb area. Furthermore, analysis on the ratios of human REP-1 expression level to endogenous cynomolgus REP-1 expression level suggests that the two doses in this study,  $5x10^{10}$  vg/eye and  $1x10^{11}$  vg/eye, are likely to provide supraphysiologic levels of human REP-1 protein in the vector exposed area of retina.

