## 6 STATISTICAL CONSIDERATIONS

Safety analyses will be performed for all participants that receive AAV2-hCHM. Summary statistics will be provided to evaluate efficacy endpoints by dose group for all evaluable subjects. Each subject's *CHM* gene sequence information will be obtained for information only. Because of the small sample size, it is not anticipated that any statistically significant correlation will be possible between a particular mutation in the *CHM* gene and safety and efficacy outcomes.

Efficacy data will be collected; however, because of the number of subjects and the size of the dosage groups it is likely that the study lacks sufficient power to reach statistical significance. If the study results in favorable safety and tolerability profile of AAV2-hCHM, as well as an indication of efficacy, follow-on studies will be proposed to more completely evaluate statistical significance and clinical applicability of this gene therapy approach.

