## 3. INVESTIGATIONAL PLAN

### 3.1 Study Design

This is an open label, non-randomized, inter-subject dose escalation safety study (Phase 1/2) of two vector doses (up to  $5x10^{10}$  vg per eye (Dose Group 1) and up to  $1x10^{11}$  vg per eye (Dose Group 2)) administered unilaterally, with at least 2 weeks between vector administrations to successive subjects for the first two subjects of a given dose group (study-wide) and at least 2 weeks between vector administrations per clinical site for the rest of the subjects in the given dose group. The eye with worse visual acuity will be injected, unless the subject prefers that eye, in which case the contralateral (non-preferred) eye will be injected.

Five subjects will be entered to Dose Group 1 and ten to Dose Group 2. All subjects must meet entry criteria detailed in the Protocol Section 3.4. Dose escalation will be contingent upon DSMB review of the safety data through at least 30 days for all subjects in the prior cohort. Subjects will be followed up for safety and efficacy evaluations for approximately 2 years post vector administration, then additional 3 years of long-term follow-up. See Appendix A for the Schedule of Assessments.

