### **3.2** Investigational Product Administration

### 3.2.1 Randomization Scheme and Study Arm Assignment

There is no randomization. All subjects will receive investigational product.

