## 4. GENERAL CONSIDERATIONS FOR DATA ANALYSIS

Due to the small sample size there are no statistical hypotheses regarding treatment effects. Rather, displays and comparisons of study results – regarding dose-related safety and efficacy among the dose cohorts – will primarily utilize descriptive statistics, as noted below.

Unless otherwise specified, continuous variables will be summarized by presenting the number of non-missing observations (n), mean, standard deviation, median, minimum, and maximum. Categorical variables will be summarized by presenting the number and percentage of subjects for each category.

Summary results will be provided for each dose cohort. All tabulations will be based on pooled data across study sites.

Analyses will be performed using SAS for Windows statistical software, version 9.2 or higher (SAS, Cary, NC), except where other software may be deemed more appropriate.

CTI will perform all efficacy and safety statistical analyses.

Subject data will be listed, sorted by dose cohort and subject number.

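### Secondary objective (a) promises to define a required dose, but two doses two-fold apart in 5 and 10 sequential, non-randomised subjects cannot identify one

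*SAP*

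**What the plan says.** SAP 2.1.2 gives the aim as "To define the dose of AAV2-hCHM required to achieve stable, or improved visual function and functional vision in subjects with choroideremia". Protocol 2.2(a) and the synopsis carry the same aim.

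The design behind it is an "inter-subject dose escalation safety study (Phase 1/2) of two vector doses" (SAP 3.1), at up to 5x10^10 and up to 1x10^11 vg per eye. On numbers: "Five subjects will be entered to Dose Group 1 and ten to Dose Group 2". On allocation: "There is no randomization. All subjects will receive investigational product" (SAP 3.2.1). Dose Group 1 is treated first, and escalation follows DSMB review (Protocol 3.2).

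On analysis, SAP 4 sets up no hypotheses and says that dose-related efficacy will be compared among cohorts mainly with descriptive statistics: "continuous variables will be summarized by presenting the number of non-missing observations (n), mean, standard deviation, median, minimum, and maximum". SAP 6.1 specifies by-subject listings by eye and cohort. SAP 6 calls all efficacy analyses exploratory, and SAP 9 reports no power calculation. Protocol 6 concedes that "it is likely that the study lacks sufficient power to reach statistical significance".

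**The concern.** To define the dose required for an effect, a trial must show that lower doses fall short and that the named dose is enough. Two levels can do that in only one pattern of results, and cohorts of this size cannot establish even that pattern with any precision. No analysis in the SAP links results to a dose, and neither document says what counts as stable or improved.

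What is at stake is how a secondary result is read. Tables giving cohort means without intervals, under an objective worded as dose-finding, would not show the reader how little the two cohorts can say about dose.

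**Working it through.** **The plan's own figure.** The only one is the sample size: 5 + 10 = 15, which agrees with the stated maximum of 15. Neither document gives an alpha, SD, effect size or responder rate. The calculations below therefore assume two-sided alpha 0.05 and no missing data (the best case), and they are illustrations only.

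**What each pattern of results would show**

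| Dose Group 1 | Dose Group 2 | About the required dose |
|---|---|---|
| works | works | no higher than the lower dose; no lower bound |
| fails | fails | not reached; not defined |
| fails | works | above the lower dose and no higher than the upper, if the gap is real and due to dose |
| works | fails | not interpretable as a dose effect without further explanation |

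Only the third row separates the doses, and it gives a two-fold bracket. It also requires showing failure in five subjects. With 0/5 responders the exact 95% upper limit is 1 − 0.025^(1/5) = 52%.

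**Continuous measure, 5 v 10**
- The standard error of the difference is SD × √(1/5 + 1/10) = 0.5477 SD. With t(0.975, 13 df) = 2.160, the 95% half-width is 2.160 × 0.5477 = 1.18 SD.
- Power comes from the noncentral t with noncentrality d/0.5477. It is 14% for d = 0.5, 27% for d = 0.8 and 39% for d = 1.0. Power of 80% needs d = 1.66.

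**Responders, two-sided Fisher exact test.** The smallest Dose Group 2 count that is significantly better:
- 0/5 v 6/10: (210 + 10)/5005 = 0.044
- 1/5 v 9/10: (50 + 1)/3003 = 0.017
- 2/5 v 10/10: 10/455 = 0.022
- 3/5 v 10/10: 10/105 = 0.095, not significant. With 4/5 or 5/5 the best possible Dose Group 2 result is further still from significance.

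**If the two doses are in truth equal.** With a true response rate of 80% in both (assumed), Dose Group 2 looks better in 39% of trials and worse in 43%. The observed rates differ by 20 points or more in 49%.

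**What is confounded with dose**
- Sequence: all of Dose Group 1 precedes Dose Group 2 (Protocol 3.2).
- Site: the SAP Revisions table records a clinical site added for Dose Group 2.
- Eligibility: the first three Dose Group 1 subjects need a central field below 30° in at least 6 of 24 meridians; everyone else needs it in any one (Protocol 3.4.1, criterion 4).
- Delivery: both doses are maxima, and some subjects may receive less volume (Protocol 3.1 and 7.3). If the full upper dose is contained in 300 µL (assumed), a delivery of 300 × 5x10^10/1x10^11 = 150 µL equals the nominal lower dose.

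**Expected separation.** Protocol 1.4.2 says that expression ratios suggest both trial doses "are likely to provide supraphysiologic levels of human REP-1 protein in the vector exposed area of retina". The data come from "one cynomolgus monkey for each of the dose groups", at 5x10^11 to 2x10^12 vg per eye. That is 5 to 20 times the upper trial dose and 10 to 40 times the lower. The finding concerns expression, not vision.

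**The case against.** The strongest reply is that the documents conceal nothing. There are no hypotheses, efficacy is exploratory, low power is admitted, and Protocol 6 leaves statistical significance and clinical applicability to later studies. The efficacy contrast that the protocol describes is injected against uninjected eye within a subject, so a between-cohort t or Fisher test at 0.05 is not the trial's own analysis. Delivered dose, bleb area and the share of viable RPE exposed are all recorded (SAP 7.1 and 7.7), so dose information may exceed two nominal points.

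Most of this stands, and it limits the point to the wording of the objective and the missing measures of precision. It does not rescue that wording. The fellow eye helps to judge effect within a dose but does not make the two cohorts comparable. No dose-response analysis of delivered dose is specified. SAP 4 does foresee comparing efficacy among cohorts, descriptively.

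Three stronger readings are tempting, and the documents do not support them.
- *A cohort difference would be reported as the required dose and carried forward.* No passage says so. The one follow-on study described concerns the second eye, to be discussed if the product is tolerated and effective in both groups; it does not depend on a required dose.
- *The protocol expects both doses to sit on a plateau.* Its language is tentative and rests on one animal per dose. Protocol 1.3.2 reports that retinal sensitivity in the UK trial correlated with dose per mm² of surviving retina, and Protocol 9.4.3 says it is unknown whether these doses suffice.
- *No result can be significant once Dose Group 1 has 3/5 responders.* This is true only for Dose Group 2 being better. In the other direction, 3/5 v 0/10 gives p = 10/455 = 0.022.

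**Conclusion.** The point holds as a mismatch between a stated objective and the design. The trial can describe outcomes at two dose levels and could detect a very large contrast: exact Fisher power is 86% for assumed responder rates of 10% v 90%. Even that would rank two tested doses, with the confounding listed above, and would not locate a required dose. For more moderate contrasts the cohorts say little, with an interval of ±1.18 SD and 39% power at 1 SD.

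The logic of the results table needs no assumption about alpha or variance, but it does read *required* as the least dose that is enough. The numerical illustrations rest on two-sided 0.05, complete data and the effect sizes and rates named. This is not a hidden power error, and the primary safety objective is not affected.

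**What to change.** 1. In the protocol synopsis, Protocol 2.2(a) and SAP 2.1.2, restate the objective as: *To describe change in visual function and functional vision at each of the two dose levels.* This also removes the undefined terms for success from the objective.
2. In SAP 4 and 6.1, name the main continuous per-eye measures and key visits (for example Day 365 and Year 2, where the measure is scheduled). Add to the listings each cohort's mean change from baseline, injected minus control eye, with a 95% interval. Half-widths would be about 2.776/√5 = 1.24 SD for five subjects and 2.262/√10 = 0.72 SD for ten. Summarise per-subject measures such as the QOL score as change from baseline. Enter these derivations in SAP 4.6, which now lists none.
3. Show the same results against the delivered dose already captured under SAP 7.1.
4. State in SAP 6 that any comparison between cohorts is non-randomised and descriptive, and that the trial does not establish a minimum or required dose.

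The cost is some added derivations and tables and a less ambitious aim. Doses, subjects and visits do not change.

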#### 2.2 Evaluations

#### **2.2.1** Efficacy Evaluations

- Visual/retinal function evaluation:
  - Visual acuity
  - Goldmann Visual Field Test (III4e isopter)
  - Humphrey visual field tests
  - Octopus kinetic visual field test (for subjects whose central visual field is >20° in at least 1 of the 24 meridians at the Screening/Baseline visit using Goldmann perimetry III4e isopter)
  - Reading speed
  - o Contrast sensitivity
  - Color vision test
  - o Microperimetry
  - Full-field light sensitivity threshold testing
- Imaging:
  - Fundus photography
  - Optical Coherence Tomography (OCT)
- Evaluation of activities of daily life:
  - Quality of Life (QOL) questionnaire

#### 2.2.2 Safety Evaluations

- Safety and tolerability assessments including but not limited to:
  - a) Adverse events (AEs)
  - b) Clinical laboratory results
    - o Hematology
    - o Chemistry panel
    - o Urinalysis
  - c) Research laboratory results:

- AAV Viral Capsid antibody
- Peripheral blood mononuclear cells (PBMC) for ELISpot assay
- Whole blood, serum and tears for vector sequences
- d) Physical exams and vital signs
- e) Ophthalmic examinations using standard instruments and methods

## 3. INVESTIGATIONAL PLAN

### 3.1 Study Design

This is an open label, non-randomized, inter-subject dose escalation safety study (Phase 1/2) of two vector doses (up to  $5x10^{10}$  vg per eye (Dose Group 1) and up to  $1x10^{11}$  vg per eye (Dose Group 2)) administered unilaterally, with at least 2 weeks between vector administrations to successive subjects for the first two subjects of a given dose group (study-wide) and at least 2 weeks between vector administrations per clinical site for the rest of the subjects in the given dose group. The eye with worse visual acuity will be injected, unless the subject prefers that eye, in which case the contralateral (non-preferred) eye will be injected.

Five subjects will be entered to Dose Group 1 and ten to Dose Group 2. All subjects must meet entry criteria detailed in the Protocol Section 3.4. Dose escalation will be contingent upon DSMB review of the safety data through at least 30 days for all subjects in the prior cohort. Subjects will be followed up for safety and efficacy evaluations for approximately 2 years post vector administration, then additional 3 years of long-term follow-up. See Appendix A for the Schedule of Assessments.

### **3.2** Investigational Product Administration

### 3.2.1 Randomization Scheme and Study Arm Assignment

There is no randomization. All subjects will receive investigational product.

### 3.2.2 Blinding

Not applicable. This is an open-label study.

### 3.2.3 Dosing Schedule

Subjects in the first cohort will be dosed with AAV2-hCHM unilaterally by single subretinal vector delivery at up to  $5x10^{10}$  vg per eye. There will be a minimum two-week interval between subject injections. In the absence of vector-related safety concerns following DSMB review of cohort 1 data through at least a minimum of 30 days post administration, cohort 2 subjects will be dosed at up to  $1x10^{11}$  vg per eye.

### **3.2.4** Subject Compliance

Subjects may withdraw from the study at any time without prejudice to their care. As much as is feasible, the study team will follow subjects after investigational product administration since this gene transfer study offers the potential of single-use, long-term treatment that cannot be practically withdrawn.

It will be documented whether or not each subject completes the clinical study, and the reason for study discontinuation including: adverse event; consent withdrawn; death; lost to follow-up; physician decision; technical problem; request for termination by Sponsor or Regulatory Authorities; and administrative or other reason. If the Investigator becomes aware of any serious, related adverse events after the subject completes or withdraws from the study, the SAE will be recorded in the source documents and entered in the study CRF. If the subject withdraws, the study procedures to be done are identical to those of the Year 2 visit evaluations.

## 4. GENERAL CONSIDERATIONS FOR DATA ANALYSIS

Due to the small sample size there are no statistical hypotheses regarding treatment effects. Rather, displays and comparisons of study results – regarding dose-related safety and efficacy among the dose cohorts – will primarily utilize descriptive statistics, as noted below.

Unless otherwise specified, continuous variables will be summarized by presenting the number of non-missing observations (n), mean, standard deviation, median, minimum, and maximum. Categorical variables will be summarized by presenting the number and percentage of subjects for each category.

Summary results will be provided for each dose cohort. All tabulations will be based on pooled data across study sites.

Analyses will be performed using SAS for Windows statistical software, version 9.2 or higher (SAS, Cary, NC), except where other software may be deemed more appropriate.

CTI will perform all efficacy and safety statistical analyses.

Subject data will be listed, sorted by dose cohort and subject number.

### 4.1 Data Quality Assurance

Spark, or its designated representative, will conduct a pre-study visit for each study site to verify the qualifications of the investigator, inspect study site facilities, become familiarized with site staff assigned to the study, and inform the investigator of responsibilities and procedures for ensuring correct study documentation.

A study coordinator at the study site will enter subject data into a remote data capture database (RDC) by completing electronic case report forms (eCRFs). All information recorded in the eCRFs for this study must be consistent with the investigator's source documentation for the study subjects. The study site will make available source documents to CTI personnel monitoring the study. The study monitor will verify consent of all subjects to participate in the study and will perform 100% source document verification of the eCRF data.

A CTI Clinical Data Associate (CDA) will review the data for discrepancies via programmed electronic consistency checks, data listings, or manually. Any discrepancies discovered via the data review process will be issued as queries in the RDC system to the study site for resolution. Once all the source verification is complete, all queries are resolved, and the database has been updated appropriately, the database will be locked and made available to CTI Biostatistics for final analysis. Data may be pulled by CTI Biostatistics for DSMB analysis at a time when source verification and query resolution is ongoing.

All SAS programs used to create analysis datasets and output will be validated by ensuring that the ".log" files are void of all errors, warnings and notes indicative of problems. Additionally, each program will be checked to ensure that it performs according to the program specification. All programs are developed and validated by separate members of the CTI Biostatistics Department.

When performing a quality control (QC) review of listings and tables output from SAS, it is not always possible to perform a 100% QC review of all fields. If a 100% QC review is not to be performed, the sample size of fields to undergo QC review may be determined by utilizing American National Standards Institute (ANSI) sampling procedures. Sampling procedures are conducted using "normal" inspection criteria (Inspection Level II, Single, and Normal) and an Acceptable Quality Level (AQL) of 0.010%. The following shows the sampling criteria:

Number of Fields	Sample Size	Accept/Reject Criteria
2-8	2	0/1
9-15	3	0/1
16-25	5	0/1
26-50	8	0/1
51-90	13	0/1
91-150	20	0/1
151-280	32	0/1
281-500	50	0/1
501-1,200	80	0/1
1,201-3,200	125	0/1
3,201-10,000	200	0/1
10,001-35,000	315	0/1
35,001-150,000	500	0/1
150,001-500,000	800	0/1
500,001-up	1,250	0/1

Single Normal sampling procedure for Acceptable Quality Level (AQL) 0.010%

